The aim of this study is to determine whether the use of a liposomal bupivacaine based periarticular injection versus a ropivacaine based periarticular injection improves pain control in patients undergoing Total Hip and Knee arthroplasty at Kootenai Health. We intend to evaluate pain control by using a Pain Score measured every four hours during hospitalization.

Primary Outcome Variable

Pain Scores as averaged over length of stay. The Pain Scale routinely used at Kootenai Health will be utilized. This is the standard 0-10 scale with 0 being no pain to 10 which is the worst possible pain the patient has experienced.

Secondary Outcome Variable

Narcotic consumption (calculated in oral morphine equivalent dose)

Length of Stay (hours)

Setting/Resources for the Study

Kootenai Health will be the setting for the surgeries while [name] clinic will be the setting for subject recruitment. Subjects will be screened and enrolled by [name]. Surgery will be performed by [name]. Other surgeons may join the study but all will be performing the same injection technique. [name] will oversee the training of the surgeons and any other key research personnel that may join the study.

Study Design

This study will employ a prospective, randomized, double-blind, study design methodology.

Study Subjects

All subjects who have been routinely referred to [name] for total hip or knee arthroplasty will be screened for inclusion into this study.

Inclusion Criteria

- 30 - 85 years of age
- Hip or knee Arthritis (osteoarthritis, post traumatic, inflammatory, and avascular necrosis)

Exclusion Criteria

- Multiple daily doses of long acting Narcotics (such as Oxycontin, MS Contin, or Fentanyl patches etc.)
- Revision surgery
- Surgical complication (femoral fracture with implant insertion)
- Inability to provide Informed Consent

Subject Recruitment/Screening/Consent

Patients will be screened and consented during a routine pre-operative office visit to discuss their pending surgery. This will take place in a private consultation room to ensure privacy. It will be made very clear to patients that their participation is voluntary and that choosing not to participate in the study will in no way affect their future care by [name] or Kootenai Health.

Study Procedures

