Total Hip and Knee arthroplasty is a standard procedure at Kootenai Health and routinely performed by the principal investigator. Patients will be randomized to either a ropivacaine based periarticular injection or a liposomal bupivacaine based periarticular injection (See Table 1).

Table 1. Periarticular Injection Assignments

Group A	Group B
20 mL Liposomal Bupivacaine	
25 mL Bupivacaine 0.5%	49.25 mL 5mg/ml Ropivacaine
1.0 mL 1:1000 Epinephrine	1.0 mL 1:1000 Epinephrine
0.8 mL Clonidine 100 mcg/mL	0.8 mL Clonidine 100 mcg/mL
13.7 mL NaCl 0.9%	13.7 mL NaCl 0.9%
1.0 mL Ketorolac (15 – 30 mg)*	1.0 mL Ketorolac (15 – 30 mg)*

*May be deleted for patients with compromised renal function

The randomization schedule will be set up using a routine alternating treatment assignment between each patient in a 1:1 pattern using an excel spreadsheet. The group assignment will be written on an order sheet and will be taken to the pharmacy where the pharmacist will mix the injection according to standard of care and as noted in Table 1. The Investigator will not be blinded to the treatment but the post-operative providers will be blinded to the randomized assignment group. An Advanced Registered Nurse Practitioner who routinely rounds on post-operative patients to evaluate their pain control will be blinded to the assignment group.

Early Withdrawal of Subjects

A patient may be withdrawn from the study prior to the expected completion of that subject for failure to adhere to protocol requirements, or subject consent withdrawal or the investigator may withdraw the patient for safety concerns. Patients may choose to withdraw from the study at any time. Data that have already been collected prior to consent withdrawal will still be used.

Statistical Plan

This is a non-inferiority trial. Therefore, the main output from the analysis above will be a 95% confidence interval for the difference between average pain scores for the hospitalization. It is anticipated that 118 130 patients will be enrolled into each cohort with an enrollment period of 3 years. A biostatistician will be consulting on the study and performing statistical calculations. Mean pain scores will be compared between the two groups within each cohort. Opioid use (morphine equivalents) will be compared from PACU admission to discharge. Length of stay, calculated in hours from the start of the surgical procedure until time of discharge, will be compared between the two groups within each cohort.

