Potential Benefits

Patients may not benefit from their participation in this study and will receive usual care for patients undergoing Total Hip and Knee arthroplasty. It is hoped that their participation will enable the investigators to determine if there are differences in pain control between the two regimens for future patients.

Potential Risks

All procedures and medications used in this study are standard of care. The risks of bupivacaine and ropivacaine are noted in the tables below and the profiles are similar for drugs of this class. Patients may receive these medications outside the setting of this research.

Ropivacaine

Most common (>10%)	Common (5% - 10%)	Rare (<5%)
Nausea	Fever	Chills
Vomiting	Back Pain	Anxiety
Low Blood Pressure	Headache	Urine retention or low urine output
	Low blood count	High blood pressure
	Bleeding	Dizziness
	Low Heart Rate	Chest pain
	Itching	Low potassium
	Pain	Allergic Reaction: hives, rash, itching; sneezing, difficulty breathing; severe dizziness, vomiting, swelling of your face, lips, tongue or throat
	“Pins and Needles” feeling	Shortness of Breath
		Urinary tract infection, urgency, incontinence
		Numbness
		Heart Attack (<1%)
		Irregular heart rate
		Yellowing of the skin and eyes
		Low Magnesium level
		Blood clots in legs and/or lungs
		Coughing
		Agitation, confusion, sleepiness, nervousness, forgetfulness, inability to sleep, hallucination, nightmares
		Nervous Disorders: Trembling, coma, convulsions, weakness, eye drooping, stupor, pain or numbness in hands and feet
		Ringing in ears
		Muscle aches
		Fainting

Liposomal Bupivacaine

Most common (>10%)	Common (2% - 10%)	Rare (less than 2%)
Nausea	Fever	Chills
Vomiting	Dizziness	Rash
Constipation	Swelling in hands or feet	Urine Retention
	Low blood count	High blood pressure
	Bleeding	Lightheadedness

	Low blood pressure	Neck pain
	Itching	Numbness and tingling in the mouth or lips
	Fast heart rate	Allergic Reaction: hives, red rash, itching; sneezing, difficulty breathing; severe dizziness, vomiting, swelling of your face, lips, tongue or throat
	Headache	Shakiness
	Inability to sleep	Low heart rate
	Muscle spasms	Irregular heart rate
	Back pain	Ringing in the ears
	Sleepiness	Blurry vision
		Low oxygen level
		Pain
		Anxiety, confusion, depression, agitation, restlessness,
		Swelling at the incision site

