The formulation of liposomal bupivacaine allows for a longer duration of action and a slower absorption into systemic circulation, avoiding high plasma concentrations. Local infiltration can result in significant system plasma concentrations for up to 96 hours; however, significant levels are not correlated with local efficacy and differ between surgical procedures. Because of the longer lasting plasma concentrations there is concern for potential drug interactions should another local anesthetic be used during this 96-hour time period. Kootenai Health recently instituted a procedure placing a colored armband on every patient receiving liposomal bupivacaine and providing written information about the drug including time the drug was given and when the 96-hour time period is over. Patients are blinded to their treatment assignment and to maintain the blind, all study patients will receive the armband and information. This will provide the same standard of care to participants randomized to the liposomal bupivacaine group and will not incur risk to those randomized to the ropivacaine group. This information will be included in the consent form.

Breach of confidentiality is a risk of this study in the transfer of data for research purposes.

Reporting of Serious Adverse Events

Reports of unanticipated adverse events will be submitted to the IRB upon discovery following the correct policies and procedures. Copies of each report and documentation of IRB notification and receipt will be kept in the Investigator's records.

Data and Safety Monitoring Plan

Because both groups are receiving well established standard of care treatment, the Principal Investigator will oversee the safety of the study. This safety monitoring plan will include careful assessment and appropriate reporting of adverse events as noted above. Ongoing evaluation of subject eligibility, adverse events, and the informed consent process will occur with compliant reporting to the IRB of protocol deviations. The Principal Investigator will closely monitor for

trends in the data or a higher than expected rate of occurrence for any adverse effect such as a higher than expected use of pain medication in either group.

In addition, a blind interim analysis of the data will be conducted by the statistician when 50% of the sample is accrued. If the results show statistically overwhelming significant differences between groups, the blind will be broken and the study stopped.

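### Other anaesthesia and local anaesthetic are neither held constant nor recorded by arm, although the operating investigator knows the arm and the 96-hour caution concerns liposomal bupivacaine only

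*Combined protocol and SAP*

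**What the plan says.** Table 1 in Study Procedures sets out the two injection mixtures. It is the only analgesic treatment that the protocol fixes. For everything else, Potential Benefits says that patients "will receive usual care for patients undergoing Total Hip and Knee arthroplasty". Nerve blocks, spinal anaesthesia and spinal additives are not named anywhere.

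On who knows the arm, Study Procedures says "The Investigator will not be blinded to the treatment but the post-operative providers will be blinded to the randomized assignment group", and describes the operation as "routinely performed by the principal investigator". It adds: "An Advanced Registered Nurse Practitioner who routinely rounds on post-operative patients to evaluate their pain control will be blinded to the assignment group". Potential Risks says that patients are blinded. Nothing is said about anaesthesia staff. Assignment is a "routine alternating treatment assignment between each patient in a 1:1 pattern", and the group is written on an order sheet that goes to the pharmacy. Study Design nevertheless calls the trial double-blind.

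Potential Risks explains that plasma levels after liposomal bupivacaine can persist for up to 96 hours and that "there is concern for potential drug interactions should another local anesthetic be used during this 96-hour time period". No matching concern is given for ropivacaine. The same paragraph adds a safeguard: "to maintain the blind, all study patients will receive the armband and information".

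The primary outcome is "Pain Scores as averaged over length of stay". Statistical Plan also compares opioid use from PACU admission and length of stay. It includes no collection of, report on, or adjustment for other anaesthesia.

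**The concern.** Any other local or regional anaesthetic given around surgery acts on the quantities the trial measures: pain scores from the first hours onward, and opioid use from the recovery unit. If its use depends on the arm, the comparison is no longer between two injections alone.

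The protocol leaves a route for this. The operating investigator knows the arm and, under alternation, can know it before the patient reaches theatre. The documents give a stated reason for caution with further local anaesthetic in one arm and none in the other. The armband and written information make staff who do not know the arm behave alike, but they cannot do so for someone who does. The information includes the time the drug was given, so it can be complete only after the injection, when choices made before or during surgery have already been taken.

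Withholding in the liposomal arm would raise pain scores there and make ropivacaine look better for a reason unrelated to the injection. The plan has no step that would show whether this happened.

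**Working it through.** **Who could act on the arm, and when**

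- *Before and during surgery.* The investigator-surgeon knows the arm. The status of anaesthesia staff is not stated. No rule or record covers other anaesthesia. Arm-dependent choices are possible.
- *After surgery.* Providers and the rounding nurse practitioner are blinded, and every study patient carries the armband and information. The caution acts alike in both arms.

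The exposure is therefore the period around surgery, and the people who know the arm.

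**Inputs for size**

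The documents give no standard deviation, margin, power, rate of other anaesthetic use or effect of such use. The planned enrolment cannot be reproduced from them. It reads 118 130 per cohort, with two groups in each cohort, so 118/2 = 59 or 130/2 = 65 per arm. Everything else below is an assumption:

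- gap between arms in use of other local or regional anaesthetic: 0 to 30 percentage points
- effect of such use on the stay-averaged score: 0.5 to 1.5 points
- SD of the stay-averaged score: 2 points

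**Bias** = gap in use × effect

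- no gap: 0 × any effect = 0
- low: 0.10 × 0.5 = 0.05
- middle: 0.20 × 1.0 = 0.20
- high: 0.30 × 1.5 = 0.45

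**Half-width of the 95% confidence interval** = 1.96 × SD × √(2/n)

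- n = 59: 1.96 × 2 × √(2/59) = 0.72
- n = 65: 1.96 × 2 × √(2/65) = 0.69

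As a share of the half-width, the low case is 0.05/0.72 = 7%. The middle case is 0.20/0.72 = 28% to 0.20/0.69 = 29%. The high case is 0.45/0.72 = 63% to 0.45/0.69 = 65%.

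**Error rates in the middle case**

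SE = 2 × √(2/59) = 0.368, or 2 × √(2/65) = 0.351.

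- Two-sided false-positive rate with no true difference = 1 − Φ(1.96 − bias/SE) + Φ(−1.96 − bias/SE). This gives 8.4% (n = 59) or 8.8% (n = 65) instead of 5%.
- Non-inferiority error at the margin, *if* ropivacaine is the test arm = Φ(bias/SE − 1.96). This gives 7.8% or 8.2% instead of 2.5%.

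A larger sample narrows the interval but leaves the bias unchanged.

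**The case against.** The strongest reply is that the mechanism is built largely on silence. The documents do not show that nerve blocks or spinal additives are used at this site, or that their use varies between patients. If use is nil or uniform, there is no bias. This stands, and it is why the range above starts at zero.

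The 96-hour period also runs forward from the injection, so most of it is post-operative, where blinded providers and the shared armband apply. In addition, Group A's own mixture contains plain bupivacaine alongside the liposomal form, so the protocol does not treat the caution as a bar to all other local anaesthetic at surgery. The caution expresses a concern and tells nobody to withhold anything. These points also stand. They reduce the exposure to choices around surgery by people who know the arm, but do not remove it.

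Three stronger readings are tempting and are not supported:

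- *The whole operating team is unblinded.* The protocol unblinds the investigator. For anaesthesia staff it says nothing, and nothing says they see the order sheet.
- *A difference could never be found afterwards.* The enrolment spreadsheet links medical record number, study number and group, so use by arm could be extracted later if the clinical record holds it. What is missing is a plan to do so.
- *Ropivacaine would wrongly be declared non-inferior.* The protocol names neither the test arm nor the margin. Bias towards ropivacaine makes the conclusion easier to reach if ropivacaine is the test arm and harder if it is the comparator.

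**Conclusion.** The point holds in a narrow form. The protocol neither equalises nor captures anaesthesia and local anaesthetic outside the injection. The surgeon-investigator knows the arm, and alternation reveals it in advance. The only stated caution about further local anaesthetic attaches to one arm. Co-analgesia around surgery could therefore differ by arm and bias pain and opioid use, towards ropivacaine if it is withheld in the liposomal arm.

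The size cannot be determined from the documents. It is 0 to 0.45 points on the 0-10 scale under the assumed gap and effect, against a half-width of about 0.7 that itself rests on an assumed SD of 2 and 59 to 65 per arm. The calculation shows what an imbalance would do; it is not evidence that one exists. A reader should not infer that blocks are in use or are being withheld. The case for change is that a cheap safeguard is absent and the result could not be defended against this question as planned.

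**What to change.** 1. State whether anaesthesia staff are blinded, and reconcile the double-blind label with the unblinded investigator.
2. Have each patient's anaesthetic plan documented before that patient's assignment can be known. Under alternation this achieves little, because the next arm is predictable, so the step requires a concealed assignment sequence.
3. Record the type of anaesthesia, any other local anaesthetic given and any departure from the documented plan, taken from the existing anaesthetic record. Report these by arm, within each cohort, beside the primary result.
4. Reconcile how the 96-hour caution in Potential Risks applies alongside the usual-care statement in Potential Benefits and the Table 1 mixture. The clinical content is the sponsor's decision.

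The cost is one protocol paragraph, a few data fields and a concealed allocation list. The downside is slightly less freedom for the clinical team once the arm is known. Departures for safety remain allowed and are recorded.

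### The plan calls itself a non-inferiority trial but sets no margin, no arm to be shown non-inferior and no deciding confidence limit, while its primary objective asks a superiority question.

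*Combined protocol and SAP*

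**What the plan says.** Three places in the protocol bear on the primary hypothesis.

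- **Statistical Plan.** "This is a non-inferiority trial. Therefore, the main output from the analysis above will be a 95% confidence interval". The interval concerns the gap between the arms in mean pain across the stay. The same section adds: "Mean pain scores will be compared between the two groups within each cohort". On enrolment it says: "It is anticipated that 118 130 patients will be enrolled into each cohort with an enrollment period of 3 years".
- **Primary Objective.** The aim is to "determine whether the use of a liposomal bupivacaine based periarticular injection versus a ropivacaine based periarticular injection improves pain control".
- **Potential Benefits.** The hope is to "determine if there are differences in pain control between the two regimens for future patients". This is general language and only supporting evidence.

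No section gives a margin, a test or reference arm, a direction of subtraction, the limit to be compared with a margin, or a rule for success. The Statistical Plan reads continuously and shows no sign of redaction. The Background calls liposomal bupivacaine expensive and its benefit disputed. That hints that ropivacaine is the arm to be shown non-inferior, but the plan never says so.

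**The concern.** Non-inferiority is concluded by comparing one named limit of a confidence interval with a margin fixed in advance. The plan supplies the interval and none of the rest. Its only directional statement, in the Primary Objective, points to superiority of liposomal bupivacaine.

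The same interval could therefore be read afterwards as liposomal bupivacaine superior, liposomal bupivacaine non-inferior, or ropivacaine non-inferior. In particular, an interval that includes 0, which fails the stated objective, could be reported as non-inferiority with a margin picked to fit. The choice matters in practice because the Background presents cost as a reason for doubting the liposomal product.

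**Working it through.** **The plan's own figure.** The enrolment of 118 or 130 per cohort cannot be reproduced, because the margin, SD, power and assumed true difference are all absent. The two adjacent numbers may come from text extraction or a tracked change, and nothing below treats them as an error.

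**Inputs**

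- From the documents: a 95% interval, 1:1 allocation, a 0–10 pain scale on which higher is worse, and 118 or 130 per cohort.
- Reading: the comparison is between two groups within each cohort, so 118 or 130 is taken as a cohort total. That gives n = 59 or 65 per arm.
- Assumptions not in the documents: SD 2 points (range 1.5 to 2.5); illustrative margins D of 0.5, 1.0 and 1.5 points.
- Sign convention: difference d = ropivacaine minus liposomal, so a positive value means more pain with ropivacaine.

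**1. Precision.** Half-width h = t(0.975, 2n−2) × SD × √(2/n). For SD 2 and n = 65: 1.979 × 2 × √(2/65) = 0.69. For n = 59 it is 0.73.

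**2. One interval, several verdicts.** Take an observed d = +0.4 with 65 per arm.

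| SD | h | 95% CI | Liposomal superior? | Liposomal non-inferior, D = 1.0? | Ropivacaine non-inferior, D = 1.0? | Ropivacaine non-inferior, D = 1.5? |
|---|---|---|---|---|---|---|
| 1.5 | 0.52 | −0.12 to +0.92 | No | Yes | Yes | Yes |
| 2.0 | 0.69 | −0.29 to +1.09 | No | Yes | No | Yes |
| 2.5 | 0.87 | −0.47 to +1.27 | No | Yes | No | Yes |

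At SD 2 or 2.5 the conclusion about ropivacaine depends entirely on which margin is applied.

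**3. A margin chosen late.** Suppose ropivacaine is truly worse by 1.0 point. The chance that the upper limit falls below D is P(T > t(0.975, 2n−2)), where T is noncentral t with noncentrality (D − 1.0) / (SD × √(2/n)).

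- D = 1.0: noncentrality 0, chance 2.5%.
- D = 1.5, SD 2: 27.0% (n = 59), 29.3% (n = 65).
- D = 1.5, SD 1.5: 43.5%, 47.1%. SD 2.5: 18.9%, 20.4%.

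**4. A direction left open.** Ropivacaine fails only if d ≥ D − h. Liposomal bupivacaine fails only if d ≤ −(D − h). If h < D, both cannot happen, so at least one arm passes whatever the data show. A simulation of 200,000 trials (SD 2, 65 per arm, D = 1.0) gave at least one pass in 100% of trials at true differences of 0, 0.5 and 1.0.

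**5. What the enrolment can support.** With a true difference of 0, one-sided 2.5% and SD 2:

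| Margin | Power, 59 per arm | Power, 65 per arm | Per arm for 80% power |
|---|---|---|---|
| 0.5 | 27.0% | 29.3% | 253 |
| 1.0 | 76.8% | 80.8% | 64 |
| 1.5 | 98.1% | 98.9% | 29 |

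The same enrolment runs from far too small to more than ample, depending on a margin the plan does not state.

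**6. The other reading of cohort.** If 118 or 130 were per arm, the half-width at SD 2 would be 0.51 or 0.49, and the chance in step 3 at D = 1.5 would be about 48% or 52%. The example in step 2 changes: with 130 per arm the interval is −0.09 to +0.89 at SD 2, so both arms are non-inferior at 1.0. At SD 1.5 it is +0.03 to +0.77, so liposomal bupivacaine is superior while ropivacaine is still non-inferior at 1.0.

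**The case against.** The strongest reply is that the intent can be inferred. Liposomal bupivacaine is described as widely adopted, costly and of doubtful benefit, so ropivacaine is the natural arm to be shown non-inferior; a biostatistician is named; and one interval can serve both questions. The word superiority never appears in the objective. The interval also remains a valid estimate, and the objective's question can be answered from it.

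Part of this stands. The 95% interval is a sound estimate, and only the non-inferiority verdict is out of reach. The inferred direction is plausible, but the Primary Objective points the other way, and granting it would still leave no margin. Naming a biostatistician delegates calculations; it does not set a decision rule.

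Three cautions about the figures are also fair.

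- The 27–29% is what any trial with a margin of 1.5 would show at a true difference of 1.0. It measures harm only if 1.0 was the right margin, and no document supports either value.
- The open-direction result is not an inflated error rate: with a fixed margin, an arm truly worse by that margin still passes only 2.5% of the time. It shows that a success criterion without a direction carries little information.
- The split verdict in the worked example depends on the SD and on how cohort is read.

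None of these removes the defect, which can be seen from the text without any arithmetic.

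**Conclusion.** The concern holds, and the plan must be corrected. Non-inferiority is declared without a margin, a designated arm or a deciding limit, and the Primary Objective asks a different question. Followed as written, the plan cannot deliver the conclusion it is named for, and it leaves the primary decision open to choice after the data are known.

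That conclusion rests on the text alone and does not depend on the SD, the illustrative margins or the reading of cohort. The size of the consequence does depend on them. At SD 2 with 59 to 65 per arm, moving the margin from 1.0 to 1.5 raises the chance of calling ropivacaine non-inferior when it is truly worse by 1.0 from 2.5% to 27–29% (19–47% over SDs of 1.5 to 2.5).

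**What to change.** Make the Primary Objective and the Statistical Plan agree before the interim look at half accrual, and before any other comparative data are seen. The investigator is not blinded to assignment, so the change should be dated, with a record of what had been seen by then. Define cohort at the same time.

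**Option A: keep non-inferiority.** Suggested text:

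> In each cohort separately, the difference is mean pain with ropivacaine minus mean pain with liposomal bupivacaine. Ropivacaine is non-inferior if the upper limit of the two-sided 95% CI is below D. Ropivacaine is superior only if the upper limit is below 0. Liposomal bupivacaine is superior if the lower limit is above 0. If non-inferiority of ropivacaine and superiority of liposomal bupivacaine both hold, both are reported.

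The sponsor sets D and justifies it on clinical grounds, not from the enrolment. The Primary Objective is reworded to ask whether ropivacaine is non-inferior to liposomal bupivacaine. If the reverse direction was intended, swap the arms throughout and say so.

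The rule was checked at an observed d = +0.75 (SD 2, 65 per arm, D = 1.5). The CI is +0.06 to +1.44: ropivacaine is non-inferior, liposomal bupivacaine is superior, both are reported, and no superiority of ropivacaine is claimed.

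**Option B: test the objective as worded.** Delete the non-inferiority sentence, test superiority, and state that an interval including 0 will not be reported as non-inferiority or equivalence.

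Under either option, state the assumed SD and the power that the planned enrolment gives in each cohort.

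**Cost.** Option B is wording only. So is Option A if the sponsor reports the power the enrolment gives. A strict margin may leave that power low: 27–29% for 0.5 points at SD 2, where 80% would need about 253 per arm in each cohort. In that case, report the low power or use Option B.

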Protocol

A Prospective, Randomized Clinical Trial of Two Periarticular Multimodal Drug Injections in Total Hip and Knee Arthroplasty

Principal Investigator

[name] MD

Version Date

June 9, 2016

Background

Perioperative pain control is a fundamental part of patient satisfaction. Many therapies are aimed at improving this critical component during a hospitalization. Current pain management techniques use several different mechanisms simultaneously and are termed "multi-modal". Multi-modal therapy has demonstrated improvement in pain control after surgery while minimizing side effects. Advancement in the understanding and practice of multimodal pain management is one of the prime reasons for shorter hospital stays.

A key component of the multimodal approach to pain management is the intra-operative surgical site injection of a local anesthetic or drug cocktail. There are many formulations used for this purpose. A formulation documented in the literature was implemented by this institution which has dropped the average length of stay dramatically. Concern over the limited half-life of the administered anesthetic and the continued need for opioid administration has led to a search for better drug formulations and administration vehicles. Recently, the FDA approval of an extended release bupivacaine called liposomal bupivacaine was thought to extend the effective half-life of the anesthetic agent and thereby prolong post-operative anesthesia. Use of liposomal bupivacaine in total joint surgery was almost universally adopted after its recent approval and has been an integral part of the "same day total joint" movement.

Upon the approval of liposomal bupivacaine by the FDA, there have been a number of studies examining the efficacy of the drug in the orthopedic patient population. Liposomal bupivacaine is expensive and adds to the burden of procedural cost. Studies, often conflicted by industry sponsorship, have suggested improvement in pain control and shortened hospitalizations with the use of liposomal bupivacaine. Other studies have raised questions about the effectiveness of this agent. Recently a randomized double blind study was performed with total knees which demonstrated no improvement in pain management with the addition of liposomal bupivacaine to the multimodal pain management protocol. This study has not been performed in the hip arthroplasty population.

Primary Objective:

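### The primary pain average has two unreconciled time windows, and the plan collects no baseline pain score to adjust for or compare by arm

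*Combined protocol and SAP*

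**What the plan says.** The protocol describes the period for the primary outcome in three places.

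- Primary Objective: pain control is evaluated "using a Pain Score measured every four hours during hospitalization".
- Primary Outcome Variable: "Pain Scores as averaged over length of stay".
- Statistical Plan: the main output is "a 95% confidence interval for the difference between average pain scores for the hospitalization".

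Hospitalization is not defined anywhere. Length of stay is defined once, in the Statistical Plan, in the sentence that sets up the secondary comparison: "Length of stay, calculated in hours from the start of the surgical procedure until time of discharge". The other secondary outcome has its own explicit start: "Opioid use (morphine equivalents) will be compared from PACU admission to discharge".

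The Background section describes the treatment under study as an "intra-operative surgical site injection of a local anesthetic or drug cocktail", so any score taken before surgery precedes treatment.

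On the analysis, the Statistical Plan states "This is a non-inferiority trial" and compares mean pain scores between groups within each cohort. It mentions no baseline pain score and no adjustment. Patients are screened and consented at a routine pre-operative office visit (Subject Recruitment/Screening/Consent). Assignment alternates from patient to patient, and the investigator is not blinded (Study Procedures).

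**The concern.** The authors gave opioid use and length of stay explicit start times but gave none to the primary outcome. The sentence that governs the primary confidence interval uses the undefined term. In ordinary use, hospitalization begins at admission. Someone extracting routine four-hourly scores on that reading could include a score taken before the injection, if one was recorded. Treatment cannot affect such a score, so averaging it in moves the difference between arms toward zero. In a non-inferiority comparison, that can make an inferior arm look acceptable. Pain and opioid use are best read together, and they would then cover different periods.

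The same pre-operative information would be useful as a baseline. With strict alternation and an unblinded investigator, the next assignment can be foreseen, so comparable arms cannot be taken for granted. A baseline pain score by arm is a direct check on this, and as a covariate it would also tighten the confidence interval. The plan collects none.

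**Working it through.** **Plan's own figure.** The Statistical Plan says "It is anticipated that 118 130 patients will be enrolled into each cohort". No margin, standard deviation or power is given, so neither number can be reproduced. Both are used below as the range for cohort size.

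**Step 1: the possible windows.**

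| Reading | Start | Could a pre-operative score enter? |
|---|---|---|
| Length of stay, as defined for the secondary outcome | Start of surgery | No |
| Hospitalization | Not stated | Only if read from admission and such a score is recorded |
| Opioid window | PACU admission | No |

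**Step 2: dilution if one pre-operative score enters.** With n post-operative scores and one pre-operative score weighted equally, and no expected difference between arms before treatment, a true difference D becomes D × n/(n+1). The loss is 1/(n+1). Four-hourly scoring gives n = hours/4. The documents give no stay lengths, so these are assumed.

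- 24 h: n = 6, loss = 1/7 = 14.3%; a true 1.0-point difference becomes 0.86.
- 48 h: n = 12, loss = 1/13 = 7.7%; a true 1.0-point difference becomes 0.92.

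If the average starts at surgery or later, the loss is zero.

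**Step 3: effect on the non-inferiority error.** Dilution also changes the variance, so the shrinkage alone does not give the error rate. Let w = n/(n+1), M the margin, and SE the standard error of the undiluted difference. Let k be the pre-operative SD divided by the SD of the post-operative average, and ρ their correlation. The standard error is multiplied by s, where s² = w² + (1−w)²k² + 2w(1−w)ρk. When the tested arm is worse by exactly M, the chance of a false claim is Φ[(1−w)(M/SE)/s − 1.96]. A margin set for 80% or 90% power at zero true difference gives M/SE = 2.80 or 3.24.

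Example (24 h, 80% power, k = 1, ρ = 0): s² = 0.735 + 0.020 = 0.755, so s = 0.869. Then 0.143 × 2.80 / 0.869 = 0.461, and Φ(0.461 − 1.96) = 0.067, against a nominal 0.025.

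Over assumed ranges (power 80-90%, k 1.0-1.5, ρ 0-0.6), the error is 0.059-0.077 at 24 h and 0.041-0.045 at 48 h. With no pre-operative score it stays at 0.025.

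**Step 4: value of a baseline covariate.** A baseline with correlation r to the outcome removes r² of the outcome variance, equivalent to N/(1−r²) − N extra patients. The range r = 0.2-0.4 is assumed.

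- r = 0.2: r² = 0.04. 118/0.96 − 118 = 4.9; 130/0.96 − 130 = 5.4.
- r = 0.4: r² = 0.16. 118/0.84 − 118 = 22.5; 130/0.84 − 130 = 24.8.

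The gain is therefore about 5 to 25 patients per cohort.

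**The case against.** The strongest reply is that the plan already excludes pre-operative scores. The outcome section averages over length of stay, and the only definition of length of stay starts at surgery. A patient cannot report pain during the operation, so the first usable score falls in PACU or later, which is close to the opioid window. This is a sound reading and probably the intended one. It does not settle the matter, because the definition belongs to a secondary outcome and the sentence governing the primary interval uses the other term.

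A reader might infer that the pain window is known to open before the injection and that the trial is therefore biased toward non-inferiority. The documents do not support that. No section says when hospitalization starts, and none says that an inpatient pre-operative score is taken. The direction is also not fixed: dilution favours a false claim only if the tested arm is truly worse. The plan names neither that arm nor a margin, and the Primary Objective asks whether liposomal bupivacaine improves pain control, a question for which dilution would be conservative.

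A reader might also infer very short stays, and hence heavier dilution, from the Background's mention of same-day joint replacement. That passage describes a wider movement and does not describe this trial's patients.

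Finally, an unadjusted comparison of means is valid without a baseline, and the gain rests on an assumed correlation. That is fair: the baseline is an inexpensive improvement, and its absence is not an error in itself. The case for it is stronger here because allocation is predictable.

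**Conclusion.** The point holds in a limited form. The primary outcome is described with two windows that are not reconciled, and the first pain score that counts is not stated. Taken alone, this is close to missing detail. Any bias is conditional on hospitalization being read from admission and on a pre-operative score being recorded. Under those conditions, one such score would cost about 14% of the difference between arms at 24 h and 8% at 48 h, both assumed stays. Its direction would depend on which arm is worse. On the start-of-surgery reading there is no dilution.

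The lack of a baseline pain score stands independently of the window question. A baseline would let the arms be compared at the start under alternating allocation. At an assumed correlation of 0.2-0.4 it would remove 4-16% of outcome variance. It would show a difference in starting pain if there is one, but would not make the allocation unpredictable.

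**What to change.** 1. Use one window in the Primary Objective, the Primary Outcome Variable section and the Statistical Plan: average only the pain scores taken from PACU admission to discharge, the same window as opioid use, and state that any pre-injection score is excluded. Settle this before the interim analysis at 50% accrual.
2. Record one 0-10 pain score at the existing pre-operative visit. Adjust the within-cohort pain comparison for it, take the 95% confidence interval from the adjusted comparison, and report the baseline score by arm.

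The cost is a few lines of wording and one extra question at a visit that every patient already attends. No extra patients or visits are needed, and the four-hourly schedule can stay as it is.
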